The study will enroll adult participants of either gender aged ≥ 18 years who receive a COVID-19 vaccine. A participant signs a participant information sheet (Informed Consent Form) to participate in the clinical trial on the day of administration the first dose of the Gam-COVID-Vac (Sputnik-V) vaccine. The physician evaluates the participant's eligibility for inclusion in the study. A rapid test for SARS-CoV-2 (BIOCREDIT COVID-19 Ag)² is carried out.

If the participant meets all inclusion criteria and does not have any non-inclusion criteria, then he is included in the study, the doctor fills out the primary medical documentation.

After inclusion in the study (Day 1, Visit 1), the participant is randomized into one of two groups: participants in group 1 receive Ergoferon according to a preventive regimen for three weeks, participants in group 2 receive Placebo for three weeks.

On a day of administration of the second Gam-COVID-Vac dose³ (Day 22, Visit 2 + 3 days), a rapid SARS-CoV-2 test (BIOCREDIT COVID-19 Ag) is performed.

After administration of the second dose of the vaccine, the participant is observed for 2 weeks. After 2 weeks, Visit 3 (telephone visit) is conducted to interview the participant about their health status (absence/presence of ARVI symptoms).

All participants are provided with classic axillary temperature thermometers. The study uses an electronic diary to record any possible deterioration in the participant's condition (if applicable) to assess efficacy, safety and reporting of adverse events. The investigator instructs the participant to complete the diary. Each participant will receive an SMS reminder once a week: "If you have any symptoms of the disease, record them in the diary. The investigator will contact you."

If within five weeks of observation the participant develops symptoms of acute respiratory viral infection (increased body temperature to febrile/subfebrile values, weakness, headache, chills, cough, sore throat, other symptoms), then the study investigator performs an unscheduled visit, during which swabs are taken from the nasopharyngeal and oropharyngeal mucosa for PCR (RT-PCR) test (in the central laboratories).

If at Visits 1 or 2 a participant without ARVI symptoms has a positive rapid test result for SARS-CoV-2, his/her oropharyngeal and nasopharyngeal swabs are also collected for PCR testing (in the central laboratory).

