² If the participant tests positive for SARS-CoV-2, he/she is not enrolled in the study. The investigator's approach should be in compliance with the current version of the guidelines "Prevention, diagnosis and treatment of a new coronavirus infection (COVID-19) by the Ministry of Health of the Russian Federation.

³ Contraindications for the second dose of the vaccine: Severe post-vaccination adverse events (anaphylaxis, severe generalized allergic reactions, convulsive disorder, fever (\geq 40°C), etc.) following the injection of the first dose of the vaccine.

If a laboratory-confirmed case of SARS-CoV-2 infection (with or without symptoms) is detected, the participant prematurely completes the study as having reached the primary endpoint.

If the PCR test for SARS-CoV-2 is positive, in accordance with the requirements of Rospotrebnadzor, the information is transferred to the health care facility to which the participant is attached, where he will be provided with the necessary medical care (according to current standards). Health care facility employees report data on COVID-19 cases (in accordance with the recommendations of the Ministry of Health of the Russian Federation and the rules of health care facilities).

Possible post-vaccination symptoms;

- general (flu-like syndrome characterized by chills, fever, arthralgia, myalgia, asthenia, malaise, headache) and local (pain at the injection site, hyperemia, swelling) symptoms that develop on the first-second day and resolve within three days;
- nausea, dyspeptic disorder, loss of appetite;
- enlarged regional lymph nodes;
- allergic reactions;
- transient increase in serum levels of liver transaminases, creatinine, and creatine phosphokinase.

These post-vaccination symptoms are not recorded as adverse events (either associated with the study product administration or developing after discontinuation); they are registered by the participant in a diary and assessed by the physician as post-vaccination complications.

Transient flu-like syndrome should not be diagnosed as ARVI, in this case a PCR test for SARS-CoV-2 is not carried out.

If the participant develops COVID-19 or is hospitalized for COVID-19, then delayed telephone visit will be performed. The duration of the visit is determined by the study investigator on a case-by-case basis.

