During the study participants are allowed to take medications for the treatment of underlying (chronic) diseases, with the exception of the drugs specified in the section "Prohibited concomitant treatment."

Inclusion and exclusion criteria

Inclusion criteria

- 1. Adults of either gender aged ≥ 18 years.
- 2. Participant has not had COVID-19 within the previous 6 months.
- 3. The participant has not been vaccinated against COVID-19 or other viral infections within the previous 6 months.
- 4. Negative result of the rapid test for SARS-CoV-2 (COVID-19 Ag).
- 5. Absence of clinical manifestations of any infectious disease, but not earlier than 14 days from its debut.
- 6. Consent to use reliable contraceptive methods during the study (for men and women of reproductive potential).
- 7. Availability of a signed information sheet and informed consent form for participation in the clinical trial.

Exclusion criteria

- 1. Presence of contraindications to vaccination:
 - hypersensitivity to any component of the vaccine or a vaccine containing similar components;
 - history of severe allergic reactions;
 - acute infectious and non-communicable diseases, exacerbation of chronic diseases.
- 2. Severe chronic hepatic and renal disorders, severe thyroid dysfunction, decompensated diabetes mellitus, severe disorders of the hematopoietic system, epilepsy and other CNS diseases, acute coronary syndrome, cerebrovascular accident, myocarditis, endocarditis, pericarditis, autoimmune diseases, or immunodeficiency.
- 3. Malabsorption syndrome, including congenital or acquired lactase or other disaccharidase deficiency, galactosemia..
- 4. Hypersensitivity to any components of study drug used in the treatment.
- 5. Pregnancy, breast-feeding; childbirth less than 3 months prior to the inclusion in the study.
- 6. Patients, who, from the investigator's point of view, will not comply with study observation requirements or study drug administration procedures.
- 7. Failure to observe the participant during the study period.
- 8. History of mental illness, alcoholism or drug abuse that the investigator's opinion will interfere with successful study procedures.
- 9. Participation in other clinical trials within 3 months prior to enrollment in the study.

- 10. Use of any medications listed in "Prohibited concomitant medications" within 4 weeks before enrollment.

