* applied onto lactose powder as a mixture of three active ethanol-water solutions of the drug substance diluted 100¹², 100³⁰, 100⁵⁰ times, respectively

Excipients: lactose monohydrate, microcrystalline cellulose – 0.03 g, magnesium stearate – 0.003 g.

Method of administration: For oral administration. One tablet twice daily. The drug is taken outside the meal (between meals or 15-30 minutes before meals). Keep the tablet in the mouth, without swallowing, until completely dissolved.

Dosage form: Tablets.

Description: White to almost white, flat- faced tablets with a score and a chamfer.

Storage conditions: At a temperature not higher than 25°C. Keep out of the reach of children.

Group 2

Name of the medicinal product: Placebo

Active ingredient: NA

Excipients: lactose monohydrate, microcrystalline cellulose, magnesium stearate.

Method of administration: For oral administration. One tablet twice daily. The drug is taken outside the meal (between meals or 15-30 minutes before meals). Keep the tablet in the mouth, without swallowing, until completely dissolved.

Dosage form: Tablets.

Description: White to almost white, flat- faced tablets with a score and a chamfer.

Storage conditions: At a temperature not higher than 25°C. Keep out of the reach of children.

Treatment duration

Ergoferon/Placebo treatment duration is 3 weeks.

Observation period

Generally, patients will be monitored for 5 weeks (screening, randomization, start of treatment - Day 1, treatment -3 weeks, follow-up period -2 weeks).

Concomitant medications

[figure not shown]
During the study, the patient may receive therapy for concomitant diseases and conditions that are not criteria for non-inclusion in this study, except for medicinal products specified in the section "Prohibited concomitant treatment."

Prohibited concomitant therapy

4 weeks prior to enrollment and during the study the following drugs are not allowed:

- 1. Antivirals (J05).
- 2. Immunostimulants, including:
 - interferon inducers (acridonoacetic acid, meglumine acridone acetate/cycloferon®, umifenovir/arbidol®, kagocel®, tiloron/amixin®, lavomax®, tilaxin®, polyadenyl acid + polyuridylic acid complex/poludan®, sodium deoxyribonucleate/derinat, etc.)
 - interferons;
 - bacterial immunomodulators (including ribomunyl®, IRS-19, imudon®, bronchomunal®, etc.);
 - pidotimod/immunorix;
 - interleukins;
 - synthetic immunostimulants (levamisole, alpha-glutamyl-tryptophan/thymogen, etc.);

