 - drug products with thymus hormones;
 - herbal immunostimulants (immunal®, etc.).
- 3. Immunosuppressants (L04).
- 4. Antitumor drugs (L01) and antitumor hormonal drugs (L02).
- 5. Immune sera and immunoglobulins (J06).
- 6. Vaccines (J07).
- 7. Corticosteroids for systemic use (H02AB).
- 8. Any unapproved medicinal product.
- 9. Drugs that previously caused hypersensitivity/allergic reactions in patient.

Study design scheme

Schedule of study procedures

Procedure/ Visit	Visit 1 (Day 1)	Visit 2 (Day 22 + 3 days)	Unscheduled visit [*]	Visit 3 «phone» ▲ (Day 35 + 3 days)
Informed consent	+			
Registration in the IVRS and assignment of a personal code	+			
Rapid test for SARS-CoV-2 (COVID-19 Ag)	+	+		
Demographics	+			
Medical history	+			
Concomitant diseases and conditions	+	+	+	+
Concomitant therapy	+	+	+	+
Nasopharyngeal and oropharyngeal (throat) swabs for PCR diagnostics	+*	+*	+	
Pregnancy test	+			
Inclusion/exclusion criteria	+			
Randomization and prescription of study therapy	+			
E-diary supply	+	+	+	+
Study drug supply	+			

				17 0001 202	
Study drug accountability,		1			
compliance assessment		Т			
Evaluation of treatment safety	+	+	+	+	
Visit completion	+	+	+	+	
Study completion [•]					
* Conducted in case of a participant's illness with COVID-19					
▲ If the participant has had COVID-19	or has been hosp	italized for COVII	D-19, the timing of	the visit is	
determined by the study investigator of	n a case-by-case b	asis.			
	C GING G H A				

* Conducted with a positive rapid test for SARS-CoV-2 (COVID-19 Ag).

◆ If a patient falls ill with COVID-19, he or she will terminate participation in the study early.

Statistical Analyses

Samples

Total set: All subjects who signed Informed Consent Form (ICF). This sample will consider all adverse events (AEs) throughout the study, including those occurred prior to the study therapy.

The sample including all enrolled and randomized patients who received at least one dose of the study drug to be used for *analysis of the study treatment safety and tolerability* (*Safety population*), as all AEs identified after the study drug administration will be recorded.

The AEs registered in patients of the *Total set* sample from the moment of signing the Informed Consent Form, but before the test drug administration will not be taken into account when analyzing the study therapy safety.

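### Gastrointestinal and allergic reactions can be left out of adverse-event recording with no time or severity limit, so a between-arm difference in them may not appear in the planned safety results

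*Combined protocol and SAP*

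**What the plan says.** The Study design section of the protocol summary lists five groups of possible post-vaccination symptoms: flu-like and local symptoms; gastrointestinal symptoms; enlarged regional lymph nodes; allergic reactions; and transient laboratory rises. It then states: "These post-vaccination symptoms are not recorded as adverse events (either associated with the study product administration or developing after discontinuation". Instead, "they are registered by the participant in a diary and assessed by the physician as post-vaccination complications".

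The only time limit in the list, "symptoms that develop on the first-second day and resolve within three days", belongs to the flu-like and local item.

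On timing, participants consent "on the day of administration the first dose of the Gam-COVID-Vac (Sputnik-V) vaccine", and the Observation period section gives "start of treatment - Day 1, treatment -3 weeks, follow-up period -2 weeks". The second vaccine dose is given at Visit 2, on Day 22 with a window of plus 3 days.

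On safety reporting, the Safety assessment item under Endpoints compares adverse events between Ergoferon and Placebo, including their relation to study drug. The Safety parameters section tabulates the adverse events that were recorded. The Safety population definition under Samples says that "all AEs identified after the study drug administration will be recorded". The electronic diary is described as a tool "to assess efficacy, safety and reporting of adverse events".

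**The concern.** The exemption reaches past ordinary vaccine reactogenicity. A flu-like reaction in the days after an injection has an obvious cause and a stated window. An allergic reaction or nausea in the second or third week of twice-daily tablets has neither, yet it is of a kind on the exempt list. The plan itself foresees that the tablet can cause such a reaction, because exclusion criterion 4 is "Hypersensitivity to any components of study drug used in the treatment".

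At stake is the part of the safety comparison that bears most on a product given alongside vaccination. Both arms are vaccinated and blinded, so vaccine reactions form a common background. An excess in one arm would point to the study drug, alone or in combination with the vaccine. That inference needs counts by arm, not a causal judgement for each event. If the reactions are neither recorded as adverse events nor tabulated by arm, the comparison is not made.

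**Working it through.** The plan states no figure on this point, so the check is mainly of text.

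**Step 1. What limits each exempt category** (Study design, list of possible post-vaccination symptoms)

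| Category | Limit stated |
|---|---|
| Flu-like and local | Onset and resolution window |
| Gastrointestinal | None |
| Lymph nodes | By site only (regional) |
| Allergic | None |
| Laboratory rises | By the word transient only |

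The count is 1 with a window + 1 limited by site + 1 limited by one word + 2 unlimited = 5. The schedule of procedures contains no blood chemistry, so the laboratory item has little practical effect.

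**Step 2. Overlap of exposures.** Vaccine dose 1 and study drug both begin on Day 1. Study drug runs for three weeks, up to about the second vaccine dose. Timing alone therefore cannot separate the two causes during treatment, and no other attribution rule is given.

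**Step 3. Route to the results.** The Safety assessment and Safety parameters sections deal with adverse events. A reaction handled as a post-vaccination complication is not recorded as one, so it does not enter those tables. Data presentation says in general terms that categorical variables are tabulated by visit. It does not mention these complications or a comparison by arm.

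**Step 4. Passages that pull the other way.** The Safety population definition says all adverse events after study drug are recorded. It can be read as a rule on population and timing, with the Study design section deciding what counts as an adverse event. Footnote 3, on contraindications to the second vaccine dose, calls anaphylaxis, severe generalised allergy and fever of 40°C or more adverse events. It can be read as placing severe reactions outside the exemption, but the exemption does not say so.

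**Step 5. What a by-arm table could show.** The reaction rates here are assumptions. With the same true rate p in both arms and n per arm, the half-width of the 95% confidence interval for the difference is 1.96 × √(2p(1−p)/n). From the planned randomised numbers, n = 1206/2 = 603 at the minimum size and 3420/2 = 1710 at the maximum. The Safety population may differ slightly.

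| Assumed p | n = 603 | n = 1710 |
|---|---|---|
| 1% | ±1.1 points | ±0.7 points |
| 5% | ±2.5 points | ±1.5 points |
| 10% | ±3.4 points | ±2.0 points |

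For example, at p = 5% and n = 603: 1.96 × √(2 × 0.05 × 0.95/603) = 1.96 × 0.01255 = 0.0246. These widths describe the precision of the missing comparison. They say nothing about whether a difference exists.

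**The case against.** The strongest defence is that the rule exempts post-vaccination symptoms, not every gastrointestinal or allergic event. A physician assesses each one, and the Safety assessment separately calls for a judgement of relation to study drug. On that reading, a late rash judged not to be due to the vaccine is still an adverse event. This stands as a possible reading. It means the plan does not guarantee that a difference would be missed. It does not remove the gap, because nothing directs the physician how to decide and sites could classify the same reaction differently.

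Second, the data are collected. The diary has a safety purpose, and the plan provides generic frequency tables and tests for two-by-two tables. This also stands: the by-arm comparison is unspecified, and the data are not lost.

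Third, the document calls itself a protocol summary. Adverse-event definitions and attribution rules may exist in a fuller protocol. That limits the point to the supplied text.

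A reader might infer three stronger things that the documents do not support:

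- *A difference certainly would not appear.* The physician's judgement and a possible fuller protocol both leave room for it to appear.
- *Anaphylaxis and other severe reactions go unrecorded.* Footnote 3 calls them adverse events. The fair criticism is that the exemption and the footnote have not been reconciled.
- *The plan deliberately exempts reactions caused by the study drug.* The parenthesis in the exemption mentions association with the study product. Set against the words on discontinuation, it reads more naturally as on-treatment versus off-treatment timing, and the Safety assessment expects drug-related events to be identified.

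**Conclusion.** The point holds in a limited form. In the supplied summary, two of five exempt categories have no onset, duration or severity limit. No rule separates vaccine from study-drug reactions, and both exposures start on Day 1. The stated safety comparison and tables use recorded adverse events only. A between-arm difference in gastrointestinal or allergic reactions may therefore not appear in the planned safety results, unless the physician judges the event not to be post-vaccination or a fuller protocol says otherwise.

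The size of any hidden difference cannot be estimated, because the documents give no reaction rates. Exempting the windowed flu-like and local reactions is a reasonable choice and is not criticised here. The matter should be fixed. Confidence is moderate, because the conclusion rests on the exemption being applied as worded and on the summary being complete on this point.

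**What to change.** **(a) Safety parameters.** Add a by-arm table in the Safety population: number and percentage of participants with each diary-recorded reaction a participant can observe (flu-like and local, gastrointestinal, lymph node, allergic), with a 95% confidence interval for the arm difference, whether or not the event is also recorded as an adverse event. Leave out laboratory rises, which a diary cannot capture.

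- From vaccine dose 1 to dose 2: all Safety population participants, with the handling of those who leave before dose 2 stated in advance.
- After dose 2: descriptive only, among those who received dose 2, with the denominator shown. Some participants never reach dose 2, including those who leave after a positive PCR, which is the primary outcome. This group is therefore selected after randomisation.

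**(b) Study design.** Limit the recording exemption for gastrointestinal and allergic reactions, for example to the window already stated for the flu-like and local item, counted from each vaccine dose. Reconcile it with the Safety population definition and with footnote 3, so that later or severe reactions are recorded as adverse events.

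**Cost.** One extra table, some additional recording by sites, and a higher reported adverse-event count in both arms. The text does not show that diary entries are coded by category or capture severity and causality, so some coding may be needed. If (b) is thought too burdensome, (a) alone would still make a between-arm difference visible.
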